- TBS tissue type: hepatic parenchyma, loose areolar connective tissue, fat, lymphatic tissue/lymph node beds, muscle or other (specify)
- Liver only TBS assessment (See 7.1.3.3)
- Documentation of concomitant medications as outlined in Section 6.4
- Total number of units used

Pre-Randomisation Procedures:

- EVARREST and SURGICEL will be prepared and available in the sterile field in the operating room, ready for administration for each subject.
- When the surgeon encounters the first appropriate TBS with mild or moderate bleeding in the hepatic parenchyma or soft tissue related to the primary operative procedure where conventional methods of control (i.e. suture, ligature, cautery) are ineffective or impractical, the subject can be considered for randomisation.

Randomisation:

- Once intra-operative eligibility is confirmed, and the TBS identified, the randomisation envelope will be opened while simultaneously starting the stopwatch will be immediately started, and recording the time on the wall clock (T_0).

For Subjects Randomised to EVARREST

The maximum size of EVARREST to be implanted is 6.9 square cm per kilogram of body weight. Where subject's body weight allows additional pads to be placed, a maximum of four units of the 4 x 4 inches (10.2 x 10.2 centimeters) EVARREST or a maximum of eight units of the 2 x 4 inches (5.1 x 10.2 centimeters) EVARREST may be implanted (left in place at the bleeding site) per subject assigned to be treated with EVARREST.

The size of the EVARREST applied should be sufficient for coverage of the entire TBS, and should overlap the TBS with a margin of 1-2 cm.

The surgeon will immediately apply firm continual manual compression over the entire bleeding area until 4 minutes from randomisation. The surgeon may use a surgical sponge (laparotomy pad or surgical gauze) to assist in providing adequate even pressure over the entire surface area.

The absolute time to haemostasis will be recorded, which is defined as the time elapsed from randomisation to the last moment in time at which detectable bleeding at the TBS is observed, i.e., complete haemostasis at the TBS.

Haemostasis will also be assessed at 4 minutes and 10 minutes and at initiation of final closure, post-randomisation for all subjects.

EVARREST should not be removed once bleeding has been stopped.

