If breakthrough bleeding occurs at the TBS at any time after application, the surgeon may re-treat with EVARREST if clinically appropriate, or revert to their standard of care. Any EVARREST re-treatment must be performed according to the Investigator's Brochure.

EVARREST Re-treatment

- If the surgeon finds the EVARREST was not applied properly (if there are folds, creases or crimps in the patch) the EVARREST pad should be removed and a new EVARREST pad applied as per the Investigator's Brochure. No matter the point of application, haemostasis must be assessed at 4 and 10 minutes from randomisation.
- If bleeding is due to insufficient coverage of the bleeding area, additional patches may be applied. Ensure that the edges overlap (by approximately 0.5 to 1 inch or 1 to 2 cm) with the existing patch.
- If bleeding is due to incomplete adherence to the tissue (where bleeding persists under the dressing), remove the patch and use a new one.
- If bleeding still occurs during or after the specified duration of compression, remove the used EVARREST and inspect the bleeding site. If no other primary hemostatic measures (i.e., standard surgical techniques) appear to be required, repeat the application procedure above with a new EVARREST.

EVARREST can only be used on a single TBS to be evaluated. If additional soft tissue/hepatic bleeding sites are identified, the surgeon should treat according to their standard of care.

For Subjects Randomised to SURGICEL

The control treatment group will be initiated with application of SURGICEL as per its Instructions for Use.

The surgeon will immediately apply firm continual manual compression over the entire bleeding area until 4 minutes from the time of randomisation.

The absolute time to haemostasis will be recorded, which is defined as the time elapsed from randomisation to the last moment in time at which there is detectable bleeding at the TBS is observed, i.e., complete haemostasis at the TBS.

Haemostasis will also be assessed at 4 minutes and 10 minutes and at initiation of final closure, post-randomisation for all subjects.

Additional SURGICEL may be used at the target bleeding site prior to the 4 minute time point if the surgeon finds the SURGICEL was improperly applied.

If haemostasis in the SURGICEL group is not achieved, or if bleeding requiring re-treatment at the TBS occurs anytime after the 4-minute assessment, the surgeon must control bleeding according to their standard of care.

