HAEMOSTASIS ASSESSMENT (TIME TABLE):

T₀	Start time when randomisation envelope is opened
T_{APP}	Time when haemostatic product is initially applied with manual compression
T₄	TBS Bleeding assessment 4 minutes following randomisation. Note: Manual compression must be maintained from application until this initial assessment.
T₁₀	TBS Bleeding assessment 10 minutes following randomisation.
T_{ABS}	Absolute time to haemostasis; as defined as the absolute time elapsed from randomisation to the last moment in time at which there is detectable bleeding at the TBS

7.1.3.1 Adverse events from start of randomisation, including any complications potentially related to bleeding and/or thrombotic events.

7.1.3.2 Additional procedural and hospital stay information will also be recorded including surgery procedural times, blood product usage, blood transfusions, ICU time, estimated blood lost, cell saver use, surgical procedure/reason for surgery and alternative/additional methods used to achieve haemostasis (if applicable).

7.1.3.3 Additional surgical details will be captured for a liver only TBS, including estimated total transected plane area; estimated transected plane area treated (0-25%, 26-50%, 51-75%, 76-100%); reason for, type and location of liver resection; hepatic parenchymal classification/type; and surgeon description of bleeding site at the TBS (area, density, arterial/venous/mixed, and characterisation of intensity of flow).

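### EVARREST may be replaced or supplemented for bleeding before the 4-minute assessment and most naturally still score as a 4-minute success, with no matching step written for SURGICEL

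*Protocol*

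**What the plan says.** **Compression.** For EVARREST, Protocol 7.1.3 says: "The surgeon will immediately apply firm continual manual compression over the entire bleeding area until 4 minutes from randomisation". The note at T4 in that section's time table adds: "Manual compression must be maintained from application until this initial assessment".

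**EVARREST re-treatment (7.1.3).** The opening sentence sets no lower time limit: "If breakthrough bleeding occurs at the TBS at any time after application, the surgeon may re-treat with EVARREST if clinically appropriate". Three bullets then deal with bleeding:
- coverage: "If bleeding is due to insufficient coverage of the bleeding area, additional patches may be applied"
- adherence: "If bleeding is due to incomplete adherence to the tissue (where bleeding persists under the dressing), remove the patch and use a new one"
- continued bleeding: "If bleeding still occurs during or after the specified duration of compression, remove the used EVARREST and inspect the bleeding site". A new pad follows, unless another primary measure seems needed.

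A separate bullet covers pads with folds, creases or crimps. It keeps both assessments timed from randomisation, whenever the pad goes on.

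**SURGICEL (7.1.3).** Extra product "may be used at the target bleeding site prior to the 4 minute time point if the surgeon finds the SURGICEL was improperly applied". Where haemostasis is not achieved, or bleeding needs re-treatment after the 4-minute assessment, the surgeon uses standard of care.

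**Scoring.** The synopsis part on additional treatment fails a subject at 4 minutes only for treatment after the 4-minute endpoint. The endpoint definition (Protocol 8.3.1, SAP 3 and 8.3) also requires that no bleeding needing treatment occur before final fascial closure, and gives no start time. SAP 7 and Table 14.1.3.4 look at bleeding from 4 minutes to closure.

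**Timing data.** T_APP in the time table is "Time when haemostatic product is initially applied with manual compression". No later application is timed there.

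**The concern.** A pad cannot be removed and the site inspected while compression is maintained, so the surgeon has two instructions that cannot both be followed. On the protocol text, EVARREST has a route to repeat the assigned product for bleeding before T4. SURGICEL has a route for misapplication only.

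Take a subject who bleeds through at 2 minutes, gets a new pad and is dry at T4. If that is a success, the 4-minute proportion in the EVARREST arm includes rescued subjects, and the control arm has no written counterpart. The surgeon knows the assignment and decides whether to re-treat. Protocol 8.3.2 says that the lower 95% limits for the two proportions and their ratio serve for inference, so a few subjects of this kind could change how the 4-minute result reads.

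**Working it through.** **1. Which score follows from the text?** Three places bear on a subject re-treated for bleeding before T4 and dry at T4.
- The synopsis rule fails only treatment after the 4-minute endpoint: success.
- SAP 7 and Table 14.1.3.4 use a window from 4 minutes to closure: success.
- The endpoint clause has no start time: it can be read as failure. It cannot literally run from time zero, because every target bleeding site (TBS) is bleeding and needs treatment at randomisation.

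Taken together, success is the more natural reading. The clause leaves some room for the other.

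**2. What is each such subject worth?** The plan has no figure to reproduce: Protocol 8.1 and SAP 8.2.1 give no formal sample size calculation. The rest is illustration.

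Inputs:
- 20 per arm, from at least 40 subjects randomised 1:1.
- EVARREST base 18/20, from 89.9% at 3 or 4 minutes in the pooled trials of Protocol 1 (20 × 0.899 = 18.0).
- Control base 10/20, from 49.4% in the same pool (20 × 0.494 = 9.9). That pool includes severe bleeding, aortic surgery and a comparator other than SURGICEL, so 8, 12 and 14 are also shown.
- Subjects rescored: 1 to 3, **assumed**. The documents give no count.

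Point estimate: 1/20 = 5 percentage points per subject.

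Clopper-Pearson lower limit (SAP 8.3), the 2.5% quantile of Beta(x, n − x + 1):
- 18/20: 68.3%
- 17/20: 62.1%
- 16/20: 56.3%
- 15/20: 50.9%

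Ratio by the Farrington-Manning score method (SAP 8.3). The limits are the values R at which

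z(R) = (p_E − R·p_C) / √[ q_E(1 − q_E)/n_E + R²·q_C(1 − q_C)/n_C ] = ±1.96,

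where q_E = R·q_C, and q_C is the smaller root of A·q² + B·q + C = 0 with A = (n_E + n_C)R, B = −(n_E·R + x_E + n_C + x_C·R), C = x_E + x_C.

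For 18/20 against 10/20 the ratio is 1.80 (1.19 to 3.05). Lower limits:

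| Control successes | EVARREST 18 | 17 | 16 | 15 |
|---|---|---|---|---|
| 8 | 1.389 | 1.282 | 1.179 | 1.080 |
| 10 | 1.194 | 1.098 | 1.007 | 0.921 |
| 12 | 1.048 | 0.961 | 0.880 | 0.803 |
| 14 | 0.933 | 0.854 | 0.781 | 0.712 |

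The largest step is 1.389 − 1.282 = 0.107 and the smallest is 0.781 − 0.712 = 0.069. Each rescored subject therefore moves the lower limit by about 0.07 to 0.11. Only EVARREST subjects are rescored here. Any control subject rescored under the same rule would move the ratio back up.

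**The case against.** The strongest reply is that the plan is more coherent than it looks: status is judged at T4, durability is judged from T4 to closure, and a re-application does not reset the clock. That stands as the likelier reading, and a reader who infers that the scoring is simply undefined goes too far. But that reading is also the one that credits a rescue before T4 as success.

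A reader might also infer that control subjects cannot be re-treated before T4. The documents do not support this. The sentence on haemostasis not being achieved with SURGICEL has no clear time of its own, standard of care is not defined to exclude more SURGICEL, Protocol 6.4.1 permits other haemostats, and the Instructions for Use and Investigator's Brochure are not at hand. The supported claim is narrower: the protocol writes out a repeat step for bleeding in one arm only.

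Nor can one conclude that the time of a re-application goes unrecorded. The listed tables time only the first application, but the case report form is not available, and SAP 10.3 lists nearly everything in the database. Table 14.1.3.6 already covers the reason for additional treatment and the treatments applied, though SAP 7 ties these to bleeding from 4 minutes.

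Other safeguards exist. Re-treatment at the TBS is reported by arm with no time limit (SAP 9.1, Table 14.3.3), so unequal re-treatment would show. The primary endpoint is also summarised with and without additional randomised treatment (SAP 8.2). Neither corrects the 4-minute proportion.

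Finally, a rule that excuses misapplication but fails poor coverage would let an unblinded surgeon's stated reason drive the score. That objection is sound, and the second count in the fix answers it.

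**Conclusion.** The conflict over compression before T4 is plain on the text. The 4-minute endpoint most naturally counts an EVARREST subject rescued before T4 as a success, and the protocol gives SURGICEL no matching step. This can favour EVARREST.

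The weight is moderate. The endpoint is secondary, the study is descriptive, the plan sets no threshold for the lower limits, and SAP 8.3 does not repeat the protocol's sentence on inference. The number of subjects affected is unknown and could be zero if compression is held as instructed.

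A reader might take the illustrated fall from 1.19 to 0.92 (control 10/20, three subjects rescored) as a forecast that the result would be overturned. It is not: it rests on an assumed count and on success rates from a different mix of trials. What holds across the illustrated range is the exchange rate per subject: 5 points on the proportion and about 0.07 to 0.11 on the ratio's lower limit. That is enough to settle the rule in advance.

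**What to change.** 1. **Scoring**, in the synopsis part on additional treatment and in SAP 8.3: *In either arm, any product or other haemostatic treatment added or replaced at the TBS for bleeding before T4 is a 4-minute failure. Only replacement of a misapplied product as described in Protocol 7.1.3 (folds, creases or crimps in EVARREST; improperly applied SURGICEL) is exempt.* Also report the 4-minute proportions and ratio with **all** pre-T4 re-applications counted as failures, so that the result does not rest on the surgeon's stated reason.

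2. **Conduct**, in Protocol 7.1.3: limit bleeding-driven EVARREST re-treatment to after the 4-minute assessment, unless the surgeon judges earlier action necessary for safety. This covers the breakthrough sentence and the coverage, adherence and continued-bleeding bullets. Put the safety and misapplication exceptions in the T4 note, for both arms.

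3. **Data**: make sure that the time and reason of any re-application before T4 are recorded in both arms, if the case report form does not already do this.

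The cost is a few sentences, one extra summary and perhaps one time field, with no more subjects or visits. The downside is that the EVARREST 4-minute proportion may be slightly lower. The SAP's change summary says that major deviations have already been assessed, so timing matters: if the rule is added after data have been seen, label it a sensitivity analysis and keep the planned scoring.

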7.1.4 Post-Surgery until Hospital Discharge

Prior to discharge, the following blood samples must be drawn and data will be recorded:

- Blood samples will be taken for Full Blood Count (FBC) with Differential and Coagulation parameters (PT, aPTT, INR).
- Physical examination as per the institution's normal procedure.
- Changes in concomitant medications.
- Date of hospital discharge (for overall Length of Stay).
- Adverse events, including any complications potentially related to bleeding and/or thrombotic events.

7.1.5 30-day Follow-Up Visit (+/- 14 days)

The following information will be recorded either at the clinical follow-up visit approximately 30 days following surgery:

- Changes in concomitant medications, including use of any blood products following hospital discharge.
- Physical examination as per the institution's normal procedure.
- Adverse events, including any complications potentially related to bleeding and/or thrombotic events.

7.2 Procedures for Handling Biological Samples

7.2.1 Laboratory Tests

All laboratory investigations for FBC and Coagulation parameters will be performed at the local hospital laboratory. The volume of blood to be taken will be determined according to the standard practices of each hospital. The normal reference ranges and laboratory accreditation certificates must be provided to ETHICON. Local labs will be performing the tests in a blinded fashion as the local labs will not be aware of the randomised treatment.

7.3 Premature Withdrawal of Subjects for the Study

All randomised subjects should be encouraged to remain in the study until they have completed the 30-day follow-up visit. Subjects and/or their parent/legal guardian may discontinue participation in the study at any time and for any reason. However, if the subject decides to discontinue participation in the study, the reason must be documented when possible. Reasons for early withdrawal include, but are not limited to:

- Consent withdrawn by the subject or parent/legal guardian;
- Subject refusal to complete study visits and/or procedures;
- Lost to follow-up: a recorded delivery letter will be sent to the subject at their last known address, after a minimum of three attempts to reach the subject by telephone have failed. If communication via certified letter is unsuccessful, the subject will be considered lost to follow-up;
- Adverse events.

Subjects who discontinue from the study prematurely will not be replaced.

8 STATISTICAL METHODS

The Data Management and Biostatistics groups of Clinical Development at ETHICON will be responsible for the overall analysis of data from this protocol. The detailed Statistical Analysis Plan (SAP) will be based on and will supplement the statistical design and analysis described in this section.

8.1 Sample Size Determination

No formal sample size determination was performed for this study, however a total of 40 randomised subjects are considered adequate to provide sufficient information to evaluate data descriptively.

8.2 Data Analysis

The categorical data will be summarized descriptively by frequencies along with associated percentages for each group. The continuous variables will be summarized descriptively by number of subjects, mean, standard deviation, minimum, and maximum for each group. If applicable, a 5% significance level will be used for any statistical tests. Two-sided 95% confidence intervals will be quoted.

8.2.1 Analysis Sets

There will be three analysis sets defined:

- Full analysis set (FAS or intent-to treat) consists of all randomised subjects. Subjects who do not complete the procedure with the use of EVARREST or SURGICEL after randomisation will be included in the FAS analysis.
- Evaluable analysis set (or per protocol) consists of all FAS subjects who have no major protocol deviations affecting the primary effectiveness endpoint and have data available for this primary effectiveness endpoint.
- Safety analysis set will consist of all subjects who received treatment.
- If any subjects are mis-randomised, the FAS and Evaluable analysis sets will summarize data as randomised, and the safety set will summarize as treated. If more than 2 subjects are mis-randomised, then the FAS and Evaluable analysis sets will also summarize data as treated.

The primary endpoint analysis will be based on the Full analysis set. The evaluable analysis will be considered supportive.

Major protocol deviations will be determined prior to database lock.

8.3 Effectiveness

8.3.1 Effectiveness Variables

The following primary endpoint will be analysed using the FAS/ITT and Evaluable set:

- Absolute time to haemostasis defined as the absolute time elapsed from randomisation to the last moment in time at which detectable bleeding at the TBS is observed.

The following secondary endpoints will be analysed using the FAS/ITT set only:

- Proportion of subjects achieving haemostatic success at 4 minutes following randomisation and no bleeding requiring treatment at the TBS occurs any time prior to final fascial closure
- Proportion of subjects achieving haemostatic success at 10 minutes following randomisation and no bleeding requiring treatment at the TBS occurs any time prior to final fascial closure
- Proportion of subjects with no re-bleeding at the TBS

The following additional analysis will be performed for the FAS and Evaluable sets: Absolute time to haemostasis will also be analysed descriptively separately for subjects who achieved haemostasis with and without additional randomised treatments being required.

8.3.2 Methods of Analysis

Descriptive statistical analysis will be conducted overall, based on treatment and by paediatric groups (1 month (\geq 28 days from birth) to <1 year and $1\leq 18$ years). Primary endpoint data will also be summarized into Infants and toddlers (28 days to 23 months), Children (2 to 11 years) and Adolescent (12 to <18 years).

Two-sided 95% confidence intervals (CIs) for median absolute time to haemostasis will be reported separately for EVARREST and SURGICEL groups. In addition, for success/failure secondary endpoints (4 and 10 minutes haemostasis endpoints), two-sided 95% CI will be reported for P_F , P_C and for ratio P_F/P_C where P_F is the proportion of success in EVARREST subjects and P_C is the proportion of success in control subjects. The lower limits of these 95% CI will be utilized for statistical inferences.

8.4 Safety

8.4.1 Safety Variables / Criteria

The following will be summarized using the Safety set:

- Incidence of adverse events that are potentially related to bleeding at the TBS;
- Incidence of adverse events that are potentially related to thrombotic events;
- Incidence of re-treatment at the TBS;
- Incidence of adverse events.
- Laboratory tests (including Haemoglobin, Haematocrit, Platelets)
- Estimated intra-operative blood loss
- Volume of blood product transfused

8.4.2 Methods of Analysis

Adverse events will be summarized descriptively by the treatment received, using Medical Dictionary for Regulatory Activities (MedDRA) terminology.

Laboratory values (including coagulation parameters) will be reported in International System (SI) units. Values and changes from baseline will be listed and summarized. Clinically significant changes will be reported as part of the AE summary.

AEs (MedDRA terminology) will also be summarized into Infants and toddlers (28 days to 23 months), Children (2 to 11 years) and Adolescent (12 to <18 years).

8.5 Interim Analyses

None.

8.6 Handling of Missing Data

It is not anticipated that there will be any data missing for treated subjects for the primary endpoint, but if there is, missing data will not be imputed for the primary analysis.

Analyses of secondary endpoints will consider missing data as failures.

9 SAFETY DEFINITIONS

9.1 Adverse event

An adverse event means any untoward medical occurrence associated with the use of a drug in humans, whether or not considered drug related. An adverse event (also referred to as an adverse experience) can be any unfavourable and unintended sign, symptom, or disease temporally associated with the use of a drug, without any judgment about causality. Since post-operative pain is an expected outcome of this type of surgery, for purposes of this study, only exacerbations of expected post-operative pain based on the Investigator's judgment should be reported as an AE.

